Smokers are at higher risk of COVID-19 hospitalizations and deaths⁸ and might thus benefit greatly from high vaccination coverage. However, evidence suggests that they may be less likely to be vaccinated, as smokers are less likely to adhere to preventive measures in general and have lower adherence to other vaccines.^{9,10} Reports of a protective role of smoking on the risk of COVID-19 infection might have also reduced the perceived risks from being infected¹¹. Evidence regarding tobacco use and COVID-19 vaccine hesitancy is mixed. Some studies have shown greater mistrust in COVID-19 vaccine benefits¹¹⁻¹⁴ and greater vaccine hesitancy and lower vaccine acceptance compared to non-smokers,^{11,15,16} while other studies have reported no differences by smoking status or lower levels of vaccine hesitancy in smokers compared to non-smokers.¹⁷⁻²⁰

Vaccine uptake, however, is a dynamic process not only influenced by trust and risk perception, but by convenience factors related to physical and geographical availability, affordability, ability to understand and appeal of immunisation services.²¹ To our knowledge, two studies from convenience samples in Singapore and Palestine have examined vaccination uptake by smoking status.^{22,23} Both studies showed that smokers had higher odds of being vaccinated.^{22,23} However, these studies are not representative of the general population and relied on self-reported vaccination status, resulting in a higher risk of selection and information bias. Spacing between vaccine doses is also relevant, as a growing body of literature suggests that smokers develop a weaker immune response to COVID-19 vaccines.²⁴

Finland developed a national COVID-19 vaccination strategy and the vaccine rollout started on December 27, 2020. Vaccinations started with priority groups (health and social care personnel and people at high risk of severe COVID-19) but eventually were expanded to the whole population aged 5 and over.²⁵ COVID-19 vaccines are provided free of charge and delivered nationwide by each municipality. Finland has administered primarily mRNA vaccines (Cominarty and Spikevax).²⁵ Vaccination coverage in the Finnish population aged 18 and older has reached 89.7% for the first dose, 87.6% for the second dose and 65.1% for the booster dose by June 14, 2022.²⁶

In this study, we will examine the association between tobacco use and COVID-19 vaccine uptake and between-dose spacing. Given conflicting results of previous studies, we expect to observe an association between tobacco use and vaccination uptake and dose-spacing, but the direction of the effect is unclear. We will expand current knowledge by examining two forms of tobacco use in Finland -smoking and smokeless tobacco use (snus)- and by analysing the spacing between vaccine doses. We will use data from nationally representative surveys in Finland linked to vaccination registries, which reduces the risk of selection and information bias.

Methods

The study protocol has been written in close accordance with the Strengthening the Reporting of Observational Studies in Epidemiology (STROBE) statement for cohort studies²⁷

Study design

The study design is a cohort study of nationally representative health surveys linked to COVID-19 vaccination data derived from the Finnish National Vaccination Register, using a unique personal identification number assigned to all residents in Finland.

Setting and participants

We will use data from two FinSote Surveys, which are cross-sectional population health surveys in Finland.

Participants in the FinSote 2018 Survey were adults aged 20 years and over derived from the Population Register of Statistics Finland, which comprises all residents in Finland. This sampling frame includes people living in institutions and military conscripts.²⁸ The survey

was based on stratified random sampling, one stratum for each 19 counties. In 2017, 3300 people were invited to participate from 18 research areas (2300 adults aged 20-74 and 1000 adults aged 75+, total sample size 59400). Data was collected between October 2, 2017, and March 3, 2018. Participants received a self-administered questionnaire in Finnish, Swedish, English or Russian, which could be returned on paper or filled in electronically. The participation rate was 45%, resulting in a total of 26422 participants.²⁸ Participants were asked for consent for registry linkage, resulting in an analytical sample of 14736 subjects.

Participants in the FinSote 2020 Survey were adults aged 20 and over derived from the Digital and Population Data Services Registry, created in Jan 2020 after the merge between the Population Register of Statistics Finland and local register offices.²⁹ This sampling frame includes all residents in Finland. The survey was based on a stratified random sample of 22 regions (2000 adults aged 20-74, 800 adults aged 75+, total sample size 61600). Data collection started on September 14, 2020, and finished on February 8, 2021. Participants received a self-administered questionnaire in Finnish, Swedish, English or Russian, which could be returned on paper or filled in electronically. The analytical sample is 28199 participants, with a participation rate of 46%. In 2020, consent to linkage was included in the overall consent, and as a result, we were able to link all participants in the analytical sample.

We will link data from FinSote 2018 and 2020 surveys to the Finnish National Vaccination Register maintained by the Finnish Institute for Health and Welfare using a unique identifier assigned to all residents in Finland. The follow-up will be between December 27, 2020 (date of the first COVID-19 vaccination in the country) until May 31, 2022 or the latest available date.

Outcomes

Our primary outcome will be the vaccination uptake of at least two doses of a COVID-19 vaccine. We will examine four secondary outcomes:

- (i) vaccination uptake of at least one dose of a COVID-19 vaccine,
- (ii) vaccination uptake of the complete COVID-19 vaccination scheme (two doses and a booster dose),
- (iii) proportion of participants with more than 7 months between the first and second COVID-19 dose, and
- (iv) proportion of participants with more than 7 months between second dose and booster dose.

We will include any approved COVID-19 vaccination in Finland by the latest available date (i.e. April 29, 2022):³⁰ COVID-19 mRNA vaccines (Comirnaty and Spikevax), recombinant vaccines (Vaxzevria, COVID-19 vaccine Janssen, COVISHIELD, Nuvaxovid, COVOVAX), and inactivated vaccines (BIBP/Sinopharm, COVAXIN, Coronavac). Participants who have received the COVID-19 vaccine Janssen would be excluded from analyses on the second dose, as the vaccine only requires a single dose.

Exposures

We will examine two forms of tobacco use: smoking and smokeless tobacco (snus) use. We will assess smoking status with the following question: Do you smoke currently (cigarettes, cigars or pipe)? (a) yes, daily, (b) occasionally, (c) not at all, (d) I have never smoked. We will create a categorical variable with the following categories: never smokers, former smokers, current occasional smokers and current daily smokers.

We will assess snus use with the following question: Do you currently use any of the following products? Snus (Swedish type moist stuff) (a) yes, daily, (b) occasionally, (c) not at all, (d) I have never used. We will create a categorical variable with the following categories: never users, former users, current users (daily and occasional combined). Data on smoking status is available for all participants, while data on snus use was available for participants aged 20-74 years old.

Potential confounders

We will adjust for several potential sociodemographic confounders: age, sex, marital status, educational tertile, and participation in social activities. All variables will be analysed at baseline. We will define marital status as those married or in a registered relationship or cohabiting versus those separated or divorced, widowed or single. We will calculate educational tertiles for each survey year using the years of education reported in the question “How many years altogether have you attended school or studied full time?”. We will analyse participants’ mother tongue using data from national registries and will categorise it into three categories: Finnish, Swedish and other. We will measure participation in social activities with a question about participation in the activities of any club, association, hobby group or religious or spiritual community. We will categorise participation into the following: no participation, occasional and active.

Potential mediators

We will take the incidence of COVID-19 infections into account (see below). We will obtain data on confirmed COVID-19 cases from the Finnish National Infectious Disease Register maintained by the Finnish Institute for Health and Welfare. Confirmed COVID-19 cases will be defined as those cases with a positive SARS-CoV-2 RT-PCR, either informed by a laboratory or by a physician as a record of an ICD-10 code U07.1 (which requires a positive SARS-CoV-2 RT-PCR). Reporting of COVID-19 positive cases was mandatory for laboratories and physicians throughout the study period.

Effect modifiers

We will examine potential effect modification by reporting stratified results by age (as a categorical variable), sex and educational level.

Data sources and measurement

[figure not shown]
Data sources and measurements for all variables were described above. More details on the exact variables can be found in the Supplementary Appendix.

Bias

Confounding bias

We will reduce the risk of confounding by adjusting for potential confounders that causally precede the exposure and are associated with the outcome. We built a directed acyclic graph to guide the identification of potential confounders and mediators (Figure 1). Adjusting for mediators can result in an underestimation of the association and potentially introduce M-bias (a type of collider bias).^{31,32}

Figure 1. Directed acyclic graph of the causal association between tobacco use and COVID-19 vaccinations uptake

A special concern were participants who had a COVID-19 infection. Tobacco use is associated with COVID-19 infection and, in turn, having a COVID-19 infection can influence the willingness to vaccinate or delay COVID-19 vaccination. Current Finnish guidelines recommend to the general adult population, after having a COVID-19 infection, to: (i) wait at least two months before getting the first COVID-19 dose, (ii) wait at least four to six months after the COVID-19 infection or the first dose, whichever happens first. People with two doses will not be given a third dose if they have had COVID-19. Having a COVID-19 infection, according to our DAG, would act as a mediator. Excluding individuals who have had the infection (or adjusting for it) would result in estimating the direct effect between tobacco use and COVID-19 vaccination uptake and not the total effect. For this reason, our main analyses will report the outcomes without adjusting for having a COVID-19 infection. In sensitivity analyses, we will report estimates stratified by COVID-19 infection status and also we will use causal inference methods (e.g. marginal structural methods and G-formula) to account for this time-varying estimate. We expect, however, that this will not make a large difference, as the COVID-19 incidence prior to the start of the COVID-19 vaccinations was very low and continued to be low until the rise of the Omicron variant in mid-December 2021.³³ In practice, this means that a very small proportion of our sample will experience a COVID-19 infection during the study period.

Selection bias

FinSote surveys 2018 and 2020 are based on a stratified random sample design that represents the Finnish population. However, non-participation in the survey could potentially introduce nonresponse bias if participants are systematically different from non-participants. For this purpose, we will take into account the complex survey design in all analyses and use the inverse probability weights (IPW) created by the Finnish Institute for Health and Welfare using a model with register-based data for the whole sample on age, sex, marital status, educational level, mother tongue and place of residence. The IPW method allows correcting for survey non-participation and the weighting factor of each participant is a combination of the inverse of the participation probability and the sampling probability. Hence, the set of weighted coefficients represents the Finnish population.³⁴

Information bias

The risk of information bias from measurement error of the exposure and confounders is inherent to most population health surveys. However, our data is almost entirely collected before assessment of the outcome, reducing the possibility that the exposure is affected by the occurrence of the outcome (i.e. that COVID-19 vaccination affects tobacco use). COVID-19 vaccination in Finland started on December 27, 2020, with a focus on health and residential care workers. The number of doses available in the first months was limited, so it is unlikely that participants from FinSote 2020 received the vaccination before the data collection. As sensitivity analyses, we will carry out the same analyses but excluding participants who have received a vaccination dose prior to February 8, 2021, when the data collection of FinSote 2020 ended. In addition, smoking status was collected relatively close to the COVID-19 vaccination, reducing (although not excluding it completely) the risk of exposure misclassification.

The COVID-19 vaccination has been implemented nationally by public providers, meaning that all COVID-19 vaccines provided have been registered in the Finnish National Vaccination Register. We estimate the risk of loss to follow-up and information bias of the outcome to be close to zero.

Study size

The sample size was determined by the available data from FinSote surveys 2018 and 2020. We consider it not necessary to provide a sample size calculation.

Quantitative variables

We described the categorisation of exposures and confounders above. We will model age as a continuous variable and tested non-linearity by comparing the linear model with penalised smoothing splines using a likelihood ratio test.³⁵ The variable years of education will be modelled as categorical to be able to account for secular changes in years of education during the study years. In other words, educational attainment increases over time and it is therefore more appropriate to calculate the educational attainment within each survey wave.

Statistical methods

We will use Poisson regression with robust standard errors to estimate the relative risk of confirmed COVID-19 cases. We will fit the following Poisson model:

$$(1) \quad \log \mu_i = \beta_0 + \beta_1 S_i + \beta_x X_i^* + \rho_1 R_a$$

where i denotes the individual, β_0 is the intercept; β_1 is the coefficient of interest for exposure to tobacco S ; a vector of covariates X^* (i.e., sex, age, marital status, years of education, mother tongue and participation in social activities); and fixed effects $\rho_1 R_a$ for wellbeing area a . We will report the exponentiated coefficient as the relative risk estimate for unadjusted and adjusted models with their corresponding 95% confidence intervals.

We will examine non-linearity between age and the outcome by comparing the linear model with penalised smoothing splines³⁵ using a likelihood ratio test with the Wald method.³⁶ We will use the model with splines if it performs better than the linear model, using a p-value of 0.05 as the threshold for this decision.

We will examine potential effect modification by reporting stratified analyses by age, sex and educational level. If there are noticeable differences, we will test for multiplicative interactions between tobacco use and sex, age and educational level by including an interaction term in equation 1. We will introduce the interaction terms one by one for each of the examined interactions. We will use a likelihood ratio test to compare the model with and without the interaction. A p-value lower than 0.05 in the likelihood ratio test will be used as an indication of the presence of an interaction. If there is evidence of an statistically significant interaction, we will include the interaction term in the final model.

Our primary method to handle missing data will be multiple imputation, given that a missing at random assumption is the most likely in our data. We will examine patterns of missing data and use multiple imputation using chained equations (MICE). This procedure will be combined with the survey design tools to take the complex sampling design into account.

In sensitivity analyses, we will report estimates using complete case analyses (i.e. taking only the complex sampling design into account). We will also report the same estimates as the main analyses, but restricting the follow-up time to when vaccination coverage reached 60% and 80%. This will allow us to understand whether these associations changed over time and also provide estimates that might be comparable to countries with lower vaccination coverage, thus increasing the external validity of our estimates.

We will analyse the data using R version 4.1.1 and include the statistical code as a Supplementary Appendix.

References

- 2 Davies, N. G. *et al.* Estimated transmissibility and impact of SARS-CoV-2 lineage B.1.1.7 in England. *Science* **372**, eabg3055, doi:doi:10.1126/science.abg3055 (2021).
- 3 Campbell, F. *et al.* Increased transmissibility and global spread of SARS-CoV-2 variants of concern as at June 2021. *Euro Surveill* **26**, doi:10.2807/1560-7917.Es.2021.26.24.2100509 (2021).
- 4 Suthar, A. B. *et al.* Public health impact of covid-19 vaccines in the US: observational study. *BMJ* **377**, e069317, doi:10.1136/bmj-2021-069317 (2022).
- 5 Krause, P. R. *et al.* SARS-CoV-2 Variants and Vaccines. *New England Journal of Medicine* **385**, 179-186, doi:10.1056/NEJMsr2105280 (2021).
- 7 Kuodi, P. *et al.* Association between vaccination status and reported incidence of post-acute COVID-19 symptoms in Israel: a cross-sectional study of patients tested between March 2020 and November 2021. *medRxiv*, 2022.2001.2005.22268800, doi:10.1101/2022.01.05.22268800 (2022).

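### FinSote 2018 lost 44.2% of its respondents at a linkage-consent step that the described weights do not cover, so the claim that weighted results represent Finland is unsupported for that wave

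*Combined protocol and SAP*

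**What the plan says.** The Setting and participants section gives a different linkage procedure for each wave. For FinSote 2018, 59,400 people were invited and 26,422 took part; then "Participants were asked for consent for registry linkage, resulting in an analytical sample of 14736 subjects". For FinSote 2020, 61,600 were invited and agreement to linkage was part of the general consent, so that "we were able to link all participants in the analytical sample", 28,199 people.

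The Selection bias section names one threat, survey non-response. It says "The IPW method allows correcting for survey non-participation" and that "the weighting factor of each participant is a combination of the inverse of the participation probability and the sampling probability". The model behind the weights uses register data on age, sex, marital status, education, mother tongue and place of residence for everyone sampled. Linkage consent does not appear in that section. It ends, for both waves together: "Hence, the set of weighted coefficients represents the Finnish population".

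The plan does not state outright that the two waves are pooled. Two phrases suggest it: "We will calculate educational tertiles for each survey year", and the intention to "calculate the educational attainment within each survey wave". Equation 1 shows no survey-wave term.

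**The concern.** Linked 2018 participants passed two filters, taking part and then agreeing to linkage. The described weights deal with the first. The second removed almost as large a share of respondents (44.2%) as the first left in (about 45% of those invited), and it applies to one wave only. The inference from the weights to the population therefore skips a stage for 2018.

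This matters because representativeness is the advance the plan claims: the Background faults earlier uptake studies as unrepresentative and more open to selection bias. If people who agree to linkage also tend to accept vaccination for reasons outside the model, the 2018 relative risk is distorted.

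No listed sensitivity analysis would show this in a pooled analysis. The plan names infection-status strata and causal methods (Confounding bias), exclusion of people vaccinated before February 8, 2021 (Information bias), and complete cases and follow-up cut at 60% and 80% coverage (Statistical methods). None is by wave. Complete-case analysis concerns missing values among included people, not respondents who were never linked.

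**Working it through.** **Counts from Setting and participants**

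- 2018 invited: 18 × (2,300 + 1,000) = 59,400, as stated. Participation: 26,422/59,400 = 44.5%, against a stated 45%.
- 2020 invited: 22 × (2,000 + 800) = 61,600, as stated. Participation: 28,199/61,600 = 45.8%, against a stated 46%.
- 2018 in the analytical sample: 14,736/26,422 = 55.8%. Absent: 26,422 − 14,736 = 11,686, or 44.2%.
- Linked share of those invited: 14,736/59,400 = 24.8% in 2018; 28,199/61,600 = 45.8% in 2020.
- Share of 2018 in the combined sample, unweighted: 14,736/42,935 = 34.3%.

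**Illustration of bias.** All inputs here are assumptions. Two-dose uptake is 0.90 in never smokers and 0.80 in smokers, so the true relative risk (RR) is 0.889. Consent differs between people later vaccinated and people not, by the same amount in both tobacco groups and beyond the covariates, with overall consent held near 55.8%. Uptake u among consenters becomes u·cv/(u·cv + (1 − u)·cu), where cv and cu are the consent proportions in the vaccinated and unvaccinated. For 57% against 47%:

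- never smokers: 0.90 × 0.57/(0.90 × 0.57 + 0.10 × 0.47) = 0.9161
- smokers: 0.80 × 0.57/(0.80 × 0.57 + 0.20 × 0.47) = 0.8291
- 2018 RR: 0.8291/0.9161 = 0.905

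Pooled uptake is s × (2018 value) + (1 − s) × (true value), with s = 0.343 from the sample shares or s = 0.5 if weighting gave the waves equal shares.

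| Consent, vaccinated / unvaccinated | 2018 RR | Pooled RR, s = 0.343 (shift) | Log shift, s = 0.343 | Log shift, s = 0.5 |
|---|---|---|---|---|
| unrelated to uptake | 0.889 | 0.889 (0) | 0 | 0 |
| 57% / 47% | 0.905 | 0.8945 (+0.006) | 0.006 | 0.009 |
| 58% / 40% | 0.918 | 0.899 (+0.010) | 0.012 | 0.017 |
| 54.5% / 66% | 0.871 | 0.883 (−0.006) | −0.007 | −0.010 |

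**Comparison with precision.** The 95% half-width of log RR is 1.96 × √(d × [0.2/(0.8·n·p) + 0.1/(0.9·n·(1 − p))]), with p the proportion of smokers and d the design effect. With p = 0.12 and d = 1.5 (assumed), it is 0.017 for n = 42,935, 0.021 for 2020 alone and 0.029 for 2018 alone. For p from 8% to 15% and d from 1 to 2, the pooled value runs from 0.013 to 0.024. At the sample shares every shift is below that range. At equal shares the pooled half-width is ½ × √(0.0294² + 0.0212²) = 0.018, just above the largest shift of 0.017.

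**Can a wave comparison isolate consent?** 2018 smoking was measured between October 2, 2017 and March 3, 2018, which is 3.24 to 2.82 years before rollout on December 27, 2020. If a fraction q of 2018 smokers had quit and had never-smoker uptake, the 2018 RR is ((1 − q) × 0.80 + q × 0.90)/0.90. That gives 0.894, 0.906 and 0.917 for q = 5%, 15% and 25%, with no consent bias at all. The 15% case is almost the same as the 57/47 case (0.905).

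**Cost in precision of 2020 alone.** By sample counts, √(42,935/28,199) = 1.23. With equal wave shares, 2/√(1 + 28,199/14,736) = 1.17.

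**The case against.** The consent step and its counts are openly disclosed, and bias is not demonstrated. Consent appears to have been given with the 2017–18 survey, well before any vaccine, so it can be tied to uptake only through shared earlier traits. Equation 1 adjusts for the measured ones: "sex, age, marital status, years of education, mother tongue and participation in social activities", plus area. The splits above treat the whole difference as residual to these, which leans towards the high side. The institute may have rebuilt the 2018 weights for linked participants. If the waves are analysed separately, 2020-only results will exist anyway. All of this stands, and it limits the point to an unsupported claim and a missing check.

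Four stronger readings are tempting, and the documents do not support them:

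- **The tobacco relative risk is biased.** Nothing in the plan shows that consent is related to uptake given the covariates.
- **44.2% refused linkage.** The text attributes the drop to the consent request but does not separate refusal from other reasons for exclusion, so 44.2% is an upper bound for refusal.
- **A difference between waves would reveal consent bias.** The older smoking measurement in 2018 can produce the same difference.
- **Correcting for consent needs the questionnaires of people who did not consent.** The weight model already uses register data for the whole sample, so inclusion in the linked sample can be modelled from those data.

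**Conclusion.** The point holds in limited form. As described, the weights combine participation and sampling probabilities only. Used that way, they leave uncorrected a selection stage that removed 44.2% of 2018 respondents, in a wave that makes up about a third of the unweighted combined sample. The population claim is therefore not supported for FinSote 2018 as written. That conclusion rests on the text and counts alone and would change only if the 2018 weights were shown to cover the linked subset.

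The effect on the adjusted relative risk is a possibility of unknown sign and probably small. The pooled shift is about 0.006 to 0.010 in either direction or none, assuming uptakes of 0.90 and 0.80, the consent splits shown, and pooling by sample share. That is within the interval half-width and changes no conclusion. The plan should be amended on this point, but the main analysis is not invalidated.

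**What to change.** 1. Report relative risks with intervals by wave, and name FinSote 2020 alone as a sensitivity analysis, since it has no separate consent step. State that a wave difference may also reflect 2018 smoking being measured 2.8 to 3.2 years before rollout, and so is not a test of consent bias.
2. For 2018, either use a weight for inclusion in the linked sample (14,736 of 59,400) from the same register-based whole-sample model, or limit the representativeness sentence in the Selection bias section to FinSote 2020. The weight needs only an indicator of who is in the linked sample. It corrects for the measured variables only, and the plan should say so. If the 2018 weights already cover the linked subset, a sentence saying how is enough for this item.

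Cost: one table by wave and an edited sentence, or a re-run of the weight model for 2018. The 2020-only intervals are about 17% to 23% wider than pooled ones, depending on the weight each wave carries. A linked-inclusion weight makes the 2018 weights more variable. It may change the adjusted relative risk little, because Equation 1 already adjusts for much the same variables.

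### Between-dose spacing is a stated aim but is measured only by one unexplained cut-off of more than 7 months, so differences below it are not measured and a null result would not show equal spacing

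*Combined protocol and SAP*

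**What the plan says.** The introduction of the combined protocol and SAP states the aim: "we will examine the association between tobacco use and COVID-19 vaccine uptake and between-dose spacing". It expects some association with uptake and "dose-spacing, but the direction of the effect is unclear". It also gives a reason for interest: "Spacing between vaccine doses is also relevant, as a growing body of literature suggests that smokers develop a weaker immune response to COVID-19 vaccines".

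Under Methods, Outcomes, spacing appears only as two secondary outcomes. The first gap is covered by (iii), "proportion of participants with more than 7 months between the first and second COVID-19 dose". For the gap before the booster, outcome (iv) is worded in parallel: "proportion of participants with more than 7 months between second dose and booster dose". The same threshold serves both intervals and is not explained. Follow-up runs from 27 December 2020 "until May 31, 2022 or the latest available date".

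The only first-to-second interval in the text is in the post-infection guidance under Confounding bias: "wait at least four to six months after the COVID-19 infection or the first dose, whichever happens first". The usual interval between doses, and its spread, are not stated.

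The Statistical methods section plans Poisson regression for relative risks. It contains no analysis of the interval in days, no median, no time-to-event model, no second cut-off and no sensitivity analysis of the 7-month threshold. The one time-related analysis re-estimates the main results with follow-up cut at the dates of 60% and 80% coverage.

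**The concern.** A single upper cut-off fits poorly with an aim whose direction is left open. A participant with 6 months between doses and one with 3 months both score zero, so neither a delay nor a shortening within that range registers. The one first-to-second wait that the plan quotes lies below the threshold.

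If most first-to-second gaps are well under 7 months, outcome (iii) counts a small tail and its relative risk rests on few events. A null or unstable estimate could then be reported as no difference in spacing although tobacco users were consistently weeks later. Even a clear relative risk would not say how much later the dose came. Both outcomes already require the dose dates, so the interval in days can be computed and is being set aside.

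**Working it through.** **Plan's own figure.** There is none to reproduce: the plan gives no sample size calculation, expected event count or interval distribution. What follows is an illustration on stated assumptions.

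**Step 1: the individual outcome.** Let T be the gap between two doses and Y = 1 if T > 7 months. If T would be below 7 months under either exposure, Y = 0 under both, whatever the difference in T. If all differences are of this kind, the true difference in the proportion with Y = 1 is 0, and a two-sided 5% test rejects only at its error rate of 0.05. This holds for (iii) and (iv) alike and needs no distributional assumption.

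**Step 2: a shift of the whole distribution, outcome (iii).** Assumptions, none from the documents: log-normal gap with median m = 2.5, 3 or 4 months and log-SD s = 0.25, 0.35 or 0.5; users' gaps longer by a ratio r = 1.1 or 1.2; 20,000 never users and 4,000 users; no design effect.

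- Never users above 7 months: p0 = 1 − Φ(ln(7/m)/s)
- Users above 7 months: p1 = 1 − Φ(ln(7/(m·r))/s)
- Binary test: z_b = (p1 − p0)/√[p(1 − p)(1/20,000 + 1/4,000)], with p the pooled proportion
- Mean log interval: z_c = ln(r)/[s·√(1/20,000 + 1/4,000)]
- Information kept relative to the mean log interval: (z_b/z_c)²
- Relative to a comparison of medians, multiply by π/2, because under this model a median carries 2/π (about 64%) of the information in the mean

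Worked case, m = 3, s = 0.35, r = 1.1:

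- p0 = 1 − Φ(0.847/0.35) = 0.77%; p1 = 1 − Φ(0.752/0.35) = 1.58%
- z_b = 4.9; z_c = 0.0953/(0.35 × 0.01732) = 15.7
- Kept: (4.92/15.72)² = 9.8%; relative to medians, 9.8% × 1.571 = 15.4%
- With unpooled variance, z_b is 3.9 and about 6% is kept

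| m (months) | s | r | p0 | p1 | z_b | z_c | Kept vs mean log | Kept vs median |
|---|---|---|---|---|---|---|---|---|
| 2.5 | 0.25 | 1.1 | 0.002% | 0.009% | 0.8 | 22.0 | 0.1% | 0.2% |
| 3 | 0.25 | 1.1 | 0.035% | 0.13% | 2.5 | 22.0 | 1.3% | 2.0% |
| 3 | 0.35 | 1.1 | 0.77% | 1.58% | 4.9 | 15.7 | 9.8% | 15.4% |
| 4 | 0.5 | 1.1 | 13.2% | 17.7% | 7.5 | 11.0 | 46.6% | 73.2% |
| 4 | 0.5 | 1.2 | 13.2% | 22.5% | 15.3 | 21.1 | 52.6% | 82.7% |

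The first row expects about 0.4 events among 4,000 users, so its z has little meaning; the event count is the message. Over all 18 combinations, pooled z_b is at least 4.4 in 14 and below 3 in four. Those four are m = 2.5 with s = 0.25 (both ratios), m = 2.5 with s = 0.35 and r = 1.1, and m = 3 with s = 0.25 and r = 1.1.

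**Step 3: a second illustration on the study's own numbers.** The two linked samples give 14,736 + 28,199 = 42,935 people. At the national second-dose coverage of 87.6%, that is about 37,611 with a second dose. Assume 12% exposed and a delay of 0.25 month in the median. With median 3 months and log-SD 0.25, about 5 exposed participants exceed 7 months. Power is then about 0.56 for the binary outcome (approximate, with so few events) against about 1.00 for the log interval. With median 4 or 6 months, binary power is at least 0.998.

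**The case against.** A reader might infer that every delay below 7 months is invisible and that the first-to-second spacing question goes largely unanswered. The documents do not support that. The blindness is exact only for people whose own gap stays under 7 months; a shift of the whole distribution also moves the tail. In the worked case the binary outcome gives z of 4.9 and a relative risk of about 2. Nor does the plan show that (iii) catches only an extreme tail: at median 4 months and log-SD 0.5, 13% of never users exceed the cut-off. With no interval distribution in the plan, neither extreme can be asserted.

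Other points on that side also stand:

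- A proportion with a long delay is a legitimate, readable outcome that fits the planned relative-risk model. It can reveal a delayed minority that a median would miss.
- A median may largely reflect rollout by priority group and municipality, so it should not be the sole basis for the conclusion.
- The benchmark matters: the loss is smaller against medians than against the mean log interval.
- No loss has been calculated for (iv), and the primary outcome is not affected.
- The Supplementary Appendix, to which the plan refers for variable details, was not available and could contain a reason for 7 months.

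The 60% and 80% coverage analyses answer less. They work in calendar time and cannot separate a late first dose from a long gap. None of these points supplies a measure of spacing below the cut-off.

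**Conclusion.** The point holds in limited form. One of the study's two stated aims rests on two indicators with a shared, unexplained threshold. Differences below it, in either direction, are not measured, and outcome (iii) may be rare. Within the assumed range, (iii) goes from practically uninformative to clearly able to detect a shift. It keeps under 1% to about 53% of the information in the mean log interval, or under 1% to about 83% relative to medians. These figures rest on the log-normal shape, the medians and spreads, the group sizes and the absence of a design effect, all of which are assumptions. What does not depend on them is the reading of a null result: a relative risk near 1 for (iii) or (iv) does not show equal spacing. This is an inexpensive improvement to secondary outcomes, not a flaw in the primary analysis.

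**What to change.** Keep (iii) and (iv) as defined and state the reason for 7 months for each interval. For each pair of doses, pre-specify a supplementary analysis of the interval in days from the dates already linked:

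- a survey-weighted, covariate-adjusted difference in interval by tobacco category (for example, in the median by quantile regression) among those with both doses;
- weighted cumulative curves of time from the earlier to the later dose by tobacco category, with the denominator stated, including how people without the later dose by the end of follow-up are handled.

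Base the statement on spacing on the interval and the tail proportion together, and say in advance that a null relative risk for either outcome will not be reported as equal spacing. The change needs no new data: some SAP wording and one further model per interval. The downside is two more secondary estimates and a slightly less simple message.
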